[figure not shown]
Title: Sleep duration and risk for obesity in Mexican American children

Number: NCT03947918

Document date: June 3, 2019

PI: [name] (1 K01 HL129087)

Subject: Study protocol

STUDY OVERVIEW

The Summertime: Kids in Motion study is a 3-week study of Mexican American children in the San Francisco area. This study includes six home visits, with the intention of making this study convenient for participants and increase study completion. The RA will make 2 home visits (Monday, Friday) and 1 phone call (Saturday) in Week 1; 1 visit (Friday) and 1 phone call (Saturday) in Week 2; and 1 phone call (Friday) and a final visit (Saturday) in Week 3. In Week 1, children will continue their normal activities. In Week 2, children will be randomized to follow a short (restricted) sleep or long (healthy) sleep schedule. In Week 3, children will be asked to follow the sleep schedule opposite from Week 2. Behavioral assessments over the three weeks will include sleep duration for (Tuesday night-Friday night), physical activity and sedentary behavior (Wednesday-Friday), and dietary intake (Thursday and Friday). A full description is provided below.

STUDY PROCEDURES AND DATA COLLECTION

Recruitment

Recruitment is critical to the study. Participants will be recruited from the community, such as community organizations, youth summer programs, churches, swat meets, parks, and UCSF clinics. Community organizations may be best to recruit from during the week, whereas parks and churches may be the best during the weekend.

When recruiting from any community organization, it will be important to contact them ahead of time over the phone. When going out into to make the initial contact, always have your SFSU student ID or UCSF badge with you and introduce yourself as a research assistant working [name], a researcher at the Univ. of California, San Francisco. You will then describe the study—a study examining how circadian behaviors such as sleep is related to physical activity and eating patterns—and that you are recruiting families with 8-10-year-old Mexican American/Mexican children. Describe the study protocol in short, and that this is a 3-week study. If the organization contact is willing to allow you to recruit participants from that location, then ask when would be the best time to catch parents so that you can speak with them and provide them with study information to participate.

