For the short sleep condition, children will be asked to sleep < 8 hrs. If parents are concerned regarding this sleep schedule, you should acknowledge their concern. Remind them that this was discussed in the study consent form, and that you will be monitoring their child for daytime drowsiness, which is a possible side effect. It is ok for their child to nap. Also, reassure them that you will be monitoring their child and calling them to make sure that they are not experiencing too much daytime drowsiness.

Child-mother pairs will continue to receive 2 daily texts or phone calls (Wednesday-Friday) as a reminder to wear the accelerometer, to complete sleep and food diaries, and to remind them of their bedtime and wake up time (as discussed).

Children in the Short Sleep Condition will be called and asked to complete the Pediatric Daytime Drowsiness Scale (Thursday). You will calculate their drowsiness score and discuss with [name] if the score is 13 or higher. The parent will also be advised. Encourage their child to take naps and that this part of the study is almost complete. If they wish to withdraw from the study, then that is ok, as their participation is voluntary.

Friday (Third home visit)

Children will be visited on Friday. Make sure that the child has the diary and food guide. Have him/her remove the accelerometer and download the accelerometer data. Check for compliance and accelerometer charge. If child is missing one day, then ask him/her to keep the accelerometer on until Sunday at noon. If they did not comply the whole week then ask them to repeat the week. If they do not want to re-wear and decide to withdraw, then thank them for their time.

After checking accelerometer compliance, you will perform a 24-hour dietary recall about Thursday. Once again, you will use the diary and the food guide. Upon completion of the visit, the family will be given a \$25 gift card for their time and participation in Week 2. Before leaving, ask when would be a good time to call on Saturday.

Saturday (Phone call)

Child participant will receive a phone call on Saturday and asked to complete a 24-hour dietary recall about Friday. Follow the same protocol as on Friday, using the diary and food guide. After this you can remind the child that he/she is free to remove the accelerometer until Tuesday (unless they are being asked to re-wear), and that you will be making a phone call on Tuesday as a reminder.

A 3-night period between sleep conditions will follow.

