
Week 3

During Week 3, participants will cross over to the opposite sleep condition. Each child will follow the opposite sleep schedule from Week 2. This means that if they were in the short sleep condition in Week 2, then they will follow the long sleep condition in Week 3. You will remind mothers about bedtime and wakeup time to make sure that their child complies with the sleep schedule. This information should be written on the front page of the *Sleep and Food Diary*, and on the *Telephone/Texting Contact Form*. On Tuesday mid-morning, mothers will be called to notify them about which sleep schedule their child will follow in Week 3.

Child-mother pairs will continue to receive 2 daily texts or phone calls (Wednesday-Friday) as a reminder to wear the accelerometer, to complete sleep and food diaries, and to remind them of their bedtime and wake up time (as discussed).

Short Sleep Condition: You will call children in the short sleep condition to administer the Daytime Drowsiness Scale. Calculate their score, and follow the same procedure as Week 2. Follow same protocol as in Week 2. Remind the mother that this is the last week of the study and that their participation is almost complete. If the parent asks to withdraw from the study, then that is ok, as their participation is voluntary.

Friday (Phone call)

On Friday, children will receive a phone call and will be asked to complete a 24-hr dietary recall for Thursday. Follow procedures as in prior the weeks using diary and food guide.

Saturday (Last home visit)

The last visit will occur on Saturday, at which time the accelerometer data will be uploaded and the child will complete a final 24-hr dietary recall for Friday. All families will complete an exit interview to discuss challenges and positive aspects to participating in the study, ideas to facilitate participation, and barriers to and facilitators of longer sleep duration. [See Exit Survey.] Upon completion, families will receive a \$40 gift card.

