Title: Sleep duration and risk for obesity in Mexican American children

Number: NCT03947918

Document date: June 16, 2020

PI: [name] (1 K01 HL129087)

Subject: Analysis plan

Analysis includes using 2-way repeated measures ANOVA. First, I will test for order effects (8 hr condition assigned first versus second) including the order main effect and the sleep-condition-by-order interaction. Non-significant order effects will be dropped and the model refit, as appropriate. If some order effects are retained in the model, then I will perform custom contrasts within each order condition, e.g., 8 v. 10.5 hrs within each order condition; and across order conditions, e.g., 8 hrs in the 8-hr-first condition versus 8 hrs in the 10.5-hr-first condition. These models will mostly focus on differences between sleep conditions.

I can use the usual sleep condition to categorize children in terms of the regular sleep duration, which can be used as either as a continuous or a categorical (e.g.,  $\leq 9$  v.  $> 9$  hrs) covariate in the regression models. This would allow testing the interaction between usual sleep duration (whether categorical or continuous) and assigned sleep duration (8 v. 10.5 hrs). If order effects are operating, i.e., significant condition-by-order interaction, then I will test 3-way interactions: condition-by-order-by-X, where X is a variable derived from the regular sleep condition, i.e., either continuous covariate or binary.

I will average Thursday and Friday dietary intake (e.g., caloric intake) and PA within week 2 and week 3, using week 1 dietary intake and PA as covariates. I will also test all 4 assessments of dietary intake and PA (Thursday and Wednesday for week 2 and week 3) in a single repeated measures model, using week 1 assessments (Thursday and Friday) as covariates. Time can be treated as a continuous or categorical variable (week 2-Wed.; week 2-Thurs; week 3-Wed.; week 3-Thurs). If categorical, I can then compare dietary intake and PA within each day of the week (e.g., Wed. and Thurs.) within each assigned sleep condition.

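### Friday contact and monitor handling differ between the two crossover weeks, which builds an avoidable week effect of unknown, probably small, size into Thursday–Friday physical activity

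*Protocol*

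**What the plan says.** **Week 2.** The protocol's section on the third home visit states "Children will be visited on Friday", followed by "Have him/her remove the accelerometer and download the accelerometer data". Wear and charge are then checked and the Thursday diet recall is done in person. At the Saturday call the instruction is "After this you can remind the child that he/she is free to remove the accelerometer until Tuesday", which implies that the monitor goes back on after the Friday download.

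**Week 3.** The Friday section reads "On Friday, children will receive a phone call and will be asked to complete a 24-hr dietary recall for Thursday". For the monitor: "The last visit will occur on Saturday, at which time the accelerometer data will be uploaded". The Study Overview gives the same schedule: "1 visit (Friday) and 1 phone call (Saturday) in Week 2; and 1 phone call (Friday) and a final visit (Saturday) in Week 3".

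**Analysis.** The third paragraph of the SAP states "I will average Thursday and Friday dietary intake (e.g., caloric intake) and PA within week 2 and week 3". It adds a second repeated-measures model that, as written, uses Wednesday and Thursday of Weeks 2 and 3. The first paragraph tests the order main effect and the condition-by-order interaction, drops them if non-significant, and otherwise moves to contrasts within each order and across orders.

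**Wear time.** The protocol asks families to note when the monitor is off (Week 1, Monday, After consent). Neither document says how those notes are used or gives a non-wear or valid-day rule.

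**The concern.** Friday is half of the averaged PA outcome in both randomised weeks, but the two Fridays are not observed alike. In Week 2 every child has a visitor, takes the monitor off for a download and does the recall face to face. In Week 3 the visit and upload fall after the last outcome day. Any PA lost to the Week 2 visit is therefore a week (period) effect put there by the contact schedule.

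In a two-period crossover a week effect cannot be separated from the condition-by-order interaction. The SAP tests that interaction and lets the result choose the analysis. A measurement difference unrelated to sleep could thus be read as an order effect, and could move the analysis from a contrast that is protected against it to contrasts that are not.

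**Working it through.** The documents give no sample size, SD, visit length or time off the monitor, so there is no stated figure to reproduce. Those inputs are assumed below and shown as ranges.

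**1. Size of the artefact.** Waking hours are 24 − 10.5 = 13.5 h (long sleep) or 24 − 8 = 16 h (short sleep). Time off is assumed to be 5–90 minutes and to carry average activity. Share of Friday = minutes ÷ (waking hours × 60); share of the Thursday–Friday mean is half of that.

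| Minutes off | Share of Friday | Share of two-day mean |
|---|---|---|
| 5 | 0.5–0.6% | 0.3% |
| 30 | 3.1–3.7% | 1.6–1.9% |
| 60 | 6.3–7.4% | 3.1–3.7% |
| 90 | 9.4–11.1% | 4.7–5.6% |

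The net difference is smaller, because the Week 3 phone recall also occupies the child.

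**2. Where it goes.** Let τ be the true short-minus-long effect, p the Week 2 artefact on the two-day mean, and f the share of children given short sleep first.

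- Short first: short-minus-long has expectation τ + p.
- Long first: τ − p.
- Pooled, with the order terms dropped: f(τ + p) + (1 − f)(τ − p) = τ + p(2f − 1). The bias is 0 at 50:50, 0.10p at 55:45 and 0.20p at 60:40.
- Week term kept, the two orders weighted equally: [(τ + p) + (τ − p)] ÷ 2 = τ at any ratio.
- Across orders (same condition, Week 2 minus Week 3): the full p.

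A simulation with 40 children, τ = −3, p = −2.5 and an SD of 10 agrees. The pooled estimate was −3.01 at 20:20 and −3.49 at 24:16, the equally weighted estimate at 24:16 was −2.98, and the within-order estimates were about −5.5 and −0.5.

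**3. Effect on the SAP's decision path.** Simulated with no sleep effect, 20 children per order, and a within-child SD of the short–long difference of 15–25% of the mean. The order test was a two-sample t-test of the differences between orders, followed by a one-sample t-test within each order.

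| Artefact (% of two-day mean) | Order test significant | Order test significant and at least one false within-order result |
|---|---|---|
| 0 | 5% | 3% |
| 1.6 | 7–10% | 4–7% |
| 3 | 11–23% | 8–17% |
| 5 | 23–53% | 17–43% |

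A 3% artefact needs 6% of Friday, that is 0.06 × 810 = 49 to 0.06 × 960 = 58 minutes. A 5% artefact needs 81 to 96 minutes. The type I error of the pooled short–long test stayed at or below about 5% at every artefact size.

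**The case against.** The strongest reply is that the weeks are crossover periods, not conditions. Each child has both sleep schedules in randomised order, and the SAP says its models focus mainly on the difference between conditions. A week effect cancels there. This stands for equal orders. The ratio of the two orders is not stated, and withdrawals could unbalance it, but the residual is only 0.20p even at 60:40.

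More of the defence also stands:

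- Both Fridays contain a Thursday recall, so the true difference is the visit minus the phone recall. The low end of the range may be the realistic one.
- The second PA model does not use Friday in Weeks 2 and 3.
- Monitor removal times are already recorded by families, and a separate activity-monitor protocol, not available here, may say more.

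Three stronger readings are tempting, and the documents do not support them.

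- A reader might infer that PA itself must differ between the weeks. Only the procedure is fixed by the schedule; the effect on PA depends on time off, behaviour during the visit and the PA metric, none of which is given.
- A reader might infer that the averaged diet outcome is distorted as well. Each week has one in-person and one phone recall, and no dietary effect can be shown.
- A reader might point out that, once the order test is significant, a false within-order result follows in roughly 70–80% of trials with a 3–5% artefact. That figure is already about 64% with no artefact, so most of it comes from testing first and then splitting by order, not from the Friday visit.

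What the reply does not answer is that the within-order and across-order contrasts are planned, and they carry the artefact in full.

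**Conclusion.** The point holds as a limited one. The two crossover weeks measure Friday differently for every child, neither document corrects for it, and the difference is avoidable. Its size is unknown and probably small.

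The harm is confined to the condition-by-order test, to the within-order and across-order contrasts that follow when order effects are retained, and to a small residual in the pooled contrast if the orders end unequal. At about half an hour off the monitor (1.6%), the false path rises from about 3% of trials to 4–7%; at 3% it reaches 8–17%. These rates rest on the assumed 40 children, the SD of 15–25%, and lost time carrying average activity with nothing offset by the Week 3 call. The documents do not support a claim that the main short–long comparison is biased.

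**What to change.** **Preferred.** Run Week 2 on the Week 3 pattern: phone recall for Thursday on Friday, then the visit, download and Friday recall on Saturday. Week 2 keeps one visit and one call, and make-up wear to Sunday noon is still possible. The cost is that wear and charge are checked a day later, when the planned wear period is nearly over, so a flat or unworn monitor is found later.

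**If the Friday visit stays.**

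- Log its start and end times, and remove the same clock window from that child's Friday PA in both Week 2 and Week 3.
- Keep the week (period) term in the model whatever its significance, so that the short–long contrast weights the two orders equally.

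This costs a visit-time log and a sentence or two in the SAP.

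PA per wear minute should not be the only metric. It would remove most of the lost-wear artefact, but the sleep conditions themselves change waking time (13.5 against 16 hours at the two targets, a difference of 2.5 hours). A rate alone would hide any effect of sleep on total activity that comes through the longer day.

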Title: Sleep duration and risk for obesity in Mexican American children

Number: NCT03947918

Document date: June 16, 2020

PI: [name] (1 K01 HL129087)

Subject: Analysis plan

Analysis includes using 2-way repeated measures ANOVA. First, I will test for order effects (8 hr condition assigned first versus second) including the order main effect and the sleep-condition-by-order interaction. Non-significant order effects will be dropped and the model refit, as appropriate. If some order effects are retained in the model, then I will perform custom contrasts within each order condition, e.g., 8 v. 10.5 hrs within each order condition; and across order conditions, e.g., 8 hrs in the 8-hr-first condition versus 8 hrs in the 10.5-hr-first condition. These models will mostly focus on differences between sleep conditions.

I can use the usual sleep condition to categorize children in terms of the regular sleep duration, which can be used as either as a continuous or a categorical (e.g.,  $\leq 9$  v.  $> 9$  hrs) covariate in the regression models. This would allow testing the interaction between usual sleep duration (whether categorical or continuous) and assigned sleep duration (8 v. 10.5 hrs). If order effects are operating, i.e., significant condition-by-order interaction, then I will test 3-way interactions: condition-by-order-by-X, where X is a variable derived from the regular sleep condition, i.e., either continuous covariate or binary.

I will average Thursday and Friday dietary intake (e.g., caloric intake) and PA within week 2 and week 3, using week 1 dietary intake and PA as covariates. I will also test all 4 assessments of dietary intake and PA (Thursday and Wednesday for week 2 and week 3) in a single repeated measures model, using week 1 assessments (Thursday and Friday) as covariates. Time can be treated as a continuous or categorical variable (week 2-Wed.; week 2-Thurs; week 3-Wed.; week 3-Thurs). If categorical, I can then compare dietary intake and PA within each day of the week (e.g., Wed. and Thurs.) within each assigned sleep condition.

Missing data, I will examine data for patterns of missingness, using Mplus. All missing data patterns, including key variables, will be examined using  $\chi^2$  and t-tests for demographic differences. MPlus will also be used to examine potential pathways to weight status because MPlus uses *full likelihood maximum likelihood* function, which does not use listwise deletion for missing data. This method is preferred as it accommodates missing data based on the assumption that data are missing at random.

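### The sleep comparison is named as a repeated-measures ANOVA with no rule for a missed day, while the SAP's likelihood method is tied explicitly only to the weight-status pathways

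*SAP*

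**What the plan says.** The first paragraph of the SAP reads "Analysis includes using 2-way repeated measures ANOVA" and directs these models mainly at the difference between sleep conditions. The third paragraph gives two analyses of diet and physical activity. One averages two days within each of Weeks 2 and 3, with Week 1 as a covariate. The other is a day-level model: "I will also test all 4 assessments of dietary intake and PA", again "using week 1 assessments (Thursday and Friday) as covariates". Neither says what happens when a day or a Week 1 value is missing.

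The SAP's missing-data paragraph starts generally: "All missing data patterns, including key variables, will be examined using" chi-square tests and "t-tests for demographic differences". It then says "MPlus will also be used to examine potential pathways to weight status", the reason given being that the software's likelihood method does not delete incomplete cases listwise. It ends "This method is preferred as it accommodates missing data based on the assumption that data are missing at random". No sentence carries the method over to the diet and activity comparison.

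The Protocol limits missing data in the field with diaries, a food guide and two daily reminders. At the Friday visits of Weeks 1 and 2 it adds longer accelerometer wear after one missed day and a repeat week after whole-week non-compliance. It states no make-up step for a missed diet recall.

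**The concern.** The SAP recognises the listwise-deletion problem and names a remedy, but does not explicitly apply it to the comparison the trial was designed to make. Two analysts could follow the text and analyse different children. One runs a classical repeated-measures ANOVA, which needs a complete record and so drops a child who missed one recall. The other fits a mixed model and keeps that child. Diet has only two recalls per week, so a single missed recall leaves the four-assessment record incomplete. What is at stake is valid data discarded, and a wider interval for the sleep contrast.

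**Working it through.** **No plan figure to reproduce.** The documents give no sample size, missingness rate or variance. Everything below is an illustration on assumed inputs.

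**Assumptions.** There are 40 children, half in each order, with two outcome days in each of Weeks 2 and 3 and two Week 1 days. (The third SAP paragraph labels these days inconsistently, which is a separate matter.) Each assessment is missing with probability p = 5%, 10% or 15%, either independently or clustered within child (beta-binomial, correlation ρ = 0.3 or 0.5). Variance shares for child / child-by-week / day are .3/.05/.65, .4/.1/.5 or .5/.1/.4.

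**Step 1: share of children kept when k values are all required** (k = 4 outcome days; k = 6 with both Week 1 days).

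- Independent: (1−p)^k. At p = 10%, 0.9^4 = 0.656 and 0.9^6 = 0.531.
- Clustered: the product over i = 0 to k−1 of (b+i)/(s+i), with s = (1−ρ)/ρ and b = (1−p)s. At p = 10%, ρ = 0.3: s = 2.333, b = 2.1, so for k = 4 it is 0.900 × 0.930 × 0.946 × 0.956 = 0.757. At ρ = 0.5 it is 0.806. For k = 6 the values are 0.706 and 0.777.

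**Step 2: standard-error ratio, complete cases against all available outcome days.** The information matrix is the sum over children of X′V⁻¹X, using only the rows each analysis keeps. X holds intercept, condition, order, day and week, and V is built from the variance shares. The ratio is the square root of the condition element of the inverse information for complete cases, divided by the same element for all available data. It is averaged over 200 simulated missingness patterns. Ranges span the variance shares and, where clustered, both correlations.

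| Missing per assessment | Four days, clustered | Four days, independent | Plus both Week 1 days, clustered | Plus both Week 1 days, independent |
|---|---|---|---|---|
| 5% | 1.03–1.05 | 1.08–1.09 | 1.04–1.07 | 1.14–1.15 |
| 10% | 1.06–1.10 | 1.18–1.19 | 1.07–1.14 | 1.32–1.34 |
| 15% | 1.09–1.15 | 1.30 | 1.12–1.22 | 1.55–1.56 |

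As lost information (1 − 1/ratio²), 1.06 is 11%, 1.10 is 17% and 1.18 is 28%. With 24 or 80 children no ratio moves by more than about 0.03. Without the week term, the independent four-day ratio at 10% is 1.167–1.176, so the result does not depend on that term.

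**Step 3: weekly averages, one day per week enough.** At 10% missing the ratio is 1.01–1.02, or 1.02–1.03 if one Week 1 day is also needed.

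**Step 4: loss of the whole second period.** If 5% to 20% of children lose it, the ratio is 1.005–1.03. A child with one condition only carries little within-child information under either method.

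**Step 5: role of Week 1.** A child's Week 1 value is the same under both conditions. In 200 simulated complete crossovers of 40 children, adding it changed the within-child estimate by less than 1e-15. For the across-order contrast, which compares different children, it cut the mean standard error from 0.273 to 0.233. Losing a child from the main contrast for want of a Week 1 value is therefore avoidable.

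**The case against.** The strongest reply is that the harm follows from a choice the SAP never makes. A reader might infer that the SAP prescribes listwise deletion for the sleep comparison. It does not. The missing-data paragraph is the only text on the subject, opens in general terms, and can be read as a preference for every analysis. The day-level analysis is called simply a repeated measures model, and time may be continuous, which fits a mixed model better than a classical ANOVA. The large ratios thus attach to the analysis least clearly named as ANOVA, while the weekly averages, stated first, lose little. All of this stands. It makes the problem an open choice and the loss illustrated, not demonstrated.

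The field safeguards also count. The whole-week non-compliance rule makes clustering plausible, so the independent figures are near an upper bound, and nothing in the documents supports 15% missing. A reader might also infer that accelerometer re-wear stops after Week 2. The Week 3 section restates no such step, but its short-sleep paragraph says to proceed as in Week 2, and whether that covers re-wear is unclear. These are collection steps, however, and do not say how an incomplete record is analysed.

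Finally, it is tempting to say that the Week 1 covariate should go. That does not follow. It is neutral for the within-child contrast with complete data, helps the across-order contrasts, and can support the missing-at-random assumption.

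**Conclusion.** The point holds as a gap in specification with a cheap remedy: minor to moderate. The named method, run in its classical form on the four-assessment data, would drop children with one missed day or one missing Week 1 value, and the SAP's own remedy is not explicitly extended to it. At an assumed 10% missing per assessment and 40 children, the cost is a standard error 6% to 10% larger under clustering and about 18% larger under independence. If both Week 1 days are also required, it is 7% to 14% larger, and up to about 33%. For weekly averages it is 1% to 3%, provided one day per week is enough, which the SAP does not say. These sizes rest wholly on assumed sample size, missingness and variance shares.

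A reader might go further and infer a biased sleep effect, for instance because children miss more days under short sleep. The documents do not show this, and a mixed model would not by itself correct it. The supported conclusion is about precision only.

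**What to change.** Add to the SAP, for the diet and activity comparison:

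> The sleep-condition comparison will be fitted as a likelihood-based linear mixed model on all available assessments, with a random child effect and, in the day-level model only, a random child-by-week effect. A child with some missed days is kept. Weekly averages use the available days. A missing Week 1 value does not remove a child; Week 1 will, for example, be modelled jointly with the outcomes.

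The child-by-week effect is confined to the day-level model because one average per week cannot separate it from residual error. The Week 1 covariate may stay. Missingness should also be compared by assigned condition and week, since the stated check covers demographics only. If the general reading of the missing-data paragraph was intended, this text simply confirms it.

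The rule "Non-significant order effects will be dropped and the model refit, as appropriate" is a separate matter; the missing-data change works with or without it.

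The cost is a few sentences and slightly more programming, with no new data. The model relies on missing at random, which the SAP already accepts.
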